**9-MONTH VISIT:**

**1.** Collect the unused Soft-Picks from the subjects in Groups A and B.

**2.** Ask the subjects to answer the Adverse Event, Taste and Compliance questionnaire.

**3.** Review medical and dental histories.

**4.** Taste Test.

**5.** Oral health examination

**6.** Retreat all PD  $\geq 5$  mm sites. Rescue therapy will be provided to sites that remain at  $\geq 5$  mm or to those demonstrating an increase in pocket depths of  $\geq 2$  mm from the baseline visit bringing them to or above the 5 mm level. Subjects will receive additional treatment (Rescue Therapy), including surgery and/or topical or systemic antibiotics, if a clinician (dentist or periodontist) decides they need it (as described in Number 9 of the 3-month Visit). Again, Rescue Therapy is standard of care for non-responsive periodontal lesions, the type depending on the clinical status of the participant. The need for Rescue Therapy (yes, no and type) will be noted in the study records and considered in the analysis of the study data.

**7.** Groups A and B will have the product, Soft-Picks, replenished and usage instructions reviewed as needed.

**8.** Make or confirm the next appointment.

**12-MONTH VISIT:**

**1.** Collect the unused Soft-Picks from the subjects in Groups A and B.

**2.** Review medical and dental histories.

**3.** Ask the subjects to answer the Adverse Event, and Compliance questionnaire.

**4.** Weight

**5.** Taste Test.

**6.** Oral health examination

7. **Collect samples: blood (FBS, HbA1c, Insulin, hs-CRP and microbiome testing, and for future testing of C-peptide, proinsulin, total GLP-1, PYY, DPP-IV, glucagon, LPS, soluble-TNF $\alpha$  RI and RII, MGO, TMAO, creatinine, and for future unknown testing), subgingival plaque, saliva, fecal, skin, and vaginal samples.**

8. **Finish Study: Participants will receive a dental cleaning (prophy) and be referred to a dentist for any necessary dental treatment needed.**

*10.2 Describe what data will be collected.*

*NOTE: For studies with multiple data collection points or long-term follow up, consider the addition of a schedule or table in your response.*

Response:

1. **Demographic information: age, date of birth, gender, racial and ethnic background**
2. **Medical History with Concomitant Medications**
3. **Dental History with Questionnaire to Assess Likelihood of Periodontal Disease**
4. **Height and Weight**
5. **Results of oral health examination and periodontal disease measurements**
6. **History of cigarette smoking and alcohol intake**
7. **Results of blood testing**
8. **Results of microbiome testing**

 *10.3 List any instruments or measurement tools used to collect data (e.g. questionnaire, interview guide, validated instrument, data collection form).*

*Include copies of these documents with your submission.*

Response:

1. **Medical History with Concomitant Medications**
2. **Dental History with Questionnaire to Assess Likelihood of Periodontal Disease**
3. **Forms – uploaded to Click as file “DM RCT Manual of Procedures”**
  - a. **Height and Weight Form**
  - b. **Blood Collection Form**
  - c. **Saliva Collection Form**

- d. **Clinical Report Form for Charting Teeth Status and Periodontal Measurement Results**
- e. **Plaque Collection Form**
- f. **Fecal Collection Information Form**
- g. **Vaginal Swab Collection Form**
- h. **Taste Test Scoring Form**

#### **4. Study Visit Checklists for each visit**

*10.4 Describe any source records that will be used to collect data about subjects (e.g. school records, electronic medical records).*

Response: AxiUm will be used to identify SDM patients with diabetes (see previous comments). **We will not use school records, medical records (electronic or otherwise), or other existing records; only those for the study. They are as follows:**

- 1. Telephone Screening Checklist**
- 2. Medical History with Concomitant Medications**
- 3. Dental History with Questionnaire to Assess Likelihood of Periodontal Disease**
- 4. AE, Taste and Compliance Assessment Questions Form**
- 5. Blood Collection Form**
- 6. Saliva Collection Form**
- 7. Plaque Collection Form**
- 8. Height and Weight Form**
- 9. Fecal Collection Information Form**
- 10. Skin Site Collection Form**
- 11. Vaginal Swab Collection Form**
- 12. Clinical Report Form for Charting Teeth Status and Periodontal Measurement Results**
- 13. Study Visit Checklists including one for Rescue Therapy and Dental Prophy**
- 14. Taste Test Scoring Form**

*10.5 Indicate whether or not **individual** subject results, such as results of investigational diagnostic tests, genetic tests, or incidental findings will be shared with subjects or others (e.g., the subject's primary care physician) and if so, describe how these will be shared.*

Response: **The results of the blood tests for diabetes status will be shared with participants when received. The results of the dental examinations will be**

**shared with participants, and their dentists, or a dentist we refer them to, if they wish. The results of the testing if samples collected during the study will not be shared with participants. Testing will be completed after it could be of use to participants and it has not been determined how specific results affect individuals.**

*10.6 Indicate whether or not study results will be shared with subjects or others, and if so, describe how these will be shared.*

**Response: Study results will not be available until participants are finished with the study. If they ask about study results later, they will be given information on where to find publications or presentation. If this study is registered at ClinicalTrials.gov they will be told of this and given the study number.**

## **11.0 Study Timelines**

*11.1 Describe the anticipated duration needed to enroll all study subjects.*

**Response: We estimate it will take 12-18 months to recruit and enroll 104 participants with complete data.**

*11.2 Describe the duration of an individual subject's participation in the study. Include length of study visits, and overall study follow-up time.*

**Response: Each participant's duration of participation is approximately 12-13 months, slightly longer if study visits are not completed as scheduled.**

*11.3 Describe the estimated duration for the investigators to complete this study (i.e. all data is collected and all analyses have been completed).*

**Response: Approximately 12-24 months.**

## **12.0 Setting**

*12.1 Describe all facilities/sites where you will be conducting research procedures. Include a description of the security and privacy of the facilities (e.g. locked facility, limited access, privacy barriers). Facility, department, and type of room are relevant. Do not abbreviate facility names.*

*NOTE: Examples of acceptable response may be: "A classroom setting in the Department of Psychology equipped with a computer with relevant survey administration software," "The angiogram suite at Buffalo General Medical Center, a fully accredited tertiary care institution within New York State with badge access," or, "Community Center meeting hall."*

**Response: The Periodontal Disease Research Center (PDRC), [name], UB, [name]. Research procedures will be performed in the operatories in the PDRC.**

**The Periodontal Disease Research Center at Buffalo was funded by the National Institutes of Health as one of their specialized clinical research centers for the study of periodontal disease. The center has been operational since 1977. The center comprises six operatories, an x-ray room, clean room for sterilizing instruments, an office, a waiting room and areas for support staff to have offices and places for meetings. Two of the operatories have doors allowing for additional privacy.**

**The PDRC's staff provides opportunities for dental and medical students, graduate students, and visiting scientists to participate in clinically oriented research projects. Since consistency of evaluations of periodontal status is necessary to limit measurement error in studies, the staff is regularly trained and calibrated in periodontal measurements. The staff also has provided training for many other examiners for other studies. As such, they are organized to provide this service.**

*12.2 For research conducted outside of UB and its affiliates, describe:*

- *Site-specific regulations or customs affecting the research*
- *Local scientific and ethical review structure*

*NOTE: This question is referring to UB affiliated research taking place outside UB, i.e. research conducted in the community, school-based research, international research, etc. It is not referring to multi-site research. UB affiliated institutions include Kaleida Health, ECMC, and Roswell Park Cancer Institute.*

**Response:**

**N/A:** This study is not conducted outside of UB or its affiliates.

## **13.0      Community-Based Participatory Research**

*13.1 Describe involvement of the community in the design and conduct of the research.*

*NOTE: Community-Based Participatory Research (CBPR) is a collaborative approach to research that equitably involves all partners in the research process and recognizes the unique strengths that each brings. CBPR begins with a research topic of importance to the community, has the aim of combining knowledge with action and achieving social change to improve health outcomes and eliminate health disparities.*

**Response:**

**N/A:** This study does not utilize CBPR.

13.2 *Describe the composition and involvement of a community advisory board.*

Response:

**N/A:** This study does not have a community advisory board.

**Response: The PI and Investigator will contribute approximately 5% effort to this study.**

**14.3** *Describe the availability of medical or psychological resources that subjects might need as a result of anticipated consequences of the human research, if applicable.*

*NOTE: One example includes: on-call availability of a counselor or psychologist for a study that screens subjects for depression.*

**Response:**

**All staff are trained in CPR and procedures are in place for emergencies. The School of Dental Medicine is also available for referrals for dental needs and referrals not addressed in the study.**

**14.4** *Describe your process to ensure that all persons assisting with the research are adequately informed about the protocol, the research procedures, and their duties and functions.*

**Response: We have extensive training sessions with staff reading the protocol, Informed Consent and all procedural SOPs before and after the training sessions. Examiners are calibrated to the Gold Standard Examiner, consistency of exams is checked, and examination of the data is completed regularly every six months. These training sessions will be documented using a Training Log (included in the revised IRB package #3). All staff who consent participants must demonstrate to a PI representative skilled in correct consenting procedures before they can consent “real” participants. Updates are provided and checks made of proficiency as needed and yearly.**

## **15.0      Other Approvals**

**15.1** *Describe any approvals that will be obtained prior to commencing the research (e.g., school, external site, funding agency, laboratory, radiation safety, or biosafety).*

**Response:**

**N/A:** This study does not require any other approvals.

## 16.0 Provisions to Protect the Privacy Interests of Subjects

16.1 *Describe how you will protect subjects' privacy interests during the course of this research.*

*NOTE: Privacy refers to an individual's right to control access to him or herself. Privacy applies to the person. Confidentiality refers to how data collected about individuals for the research will be protected by the researcher from release. Confidentiality applies to the data.*

*Examples of appropriate responses include: "participant only meets with a study coordinator in a classroom setting where no one can overhear", or "the participant is reminded that they are free to refuse to answer any questions that they do not feel comfortable answering."*

Response:

Potential and enrolled participants will interact with the study staff, dentists, registered dental hygienists, dental assistants, laboratory technicians, research associates and data manager. Participants may choose not to answer questions, but if those questions provide critical information needed to answer the research questions, the person will not be allowed to remain in the study. When exams are performed, privacy is provided via individual examination rooms; when participants have samples such as saliva and plaque collected, they are provided privacy from the view of others; blood is collected and height and weight measured out of the view of others as well.

Participants are told they may withdraw from the study at any time with no adverse effects on them. They are told we need certain data and that data need is explained prior to enrollment (at the time of consenting).

16.2 *Indicate how the research team is permitted to access any sources of information about the subjects.*

*NOTE: Examples of appropriate responses include: school permission for review of records, consent of the subject, HIPAA waiver. This question does apply to records reviews.*

Response: **Consent of the participant.**

## 17.0 Data Management and Analysis

17.1 *Describe the data analysis plan, including any statistical procedures. This section applies to both quantitative and qualitative analysis.*

Response:

**16S rRNA Microbiome Sequencing:** Samples will be analyzed to determine their bacterial composition using MiSeq (Illumina, Inc.) metagenomic sequencing technology, which is available through the Next-Generation

**Sequencing and Expression Analysis Core Laboratory.** This method can evaluate the bacterial composition of the microbiome, including those not previously cultivated. We will sequence V4 hyper-variable region of the 16S rRNA gene specific for bacterial analyses. Briefly, bacterial DNA will be isolated from all samples and will be processed by polymerase chain reaction (PCR) with control samples into sequencing libraries compatible with the MiSeq sequencer. There are techniques to tag specific samples so that every participant sample can be independently characterized. We will incorporate quality assurance checks on the microbiome analyses by using standardized mock plaque and other sample controls containing known oral organisms, as well as standard reagent control samples and negative controls. We will process the control samples with participant samples using the same procedures to determine if any bias is introduced in the DNA preparation, amplification or sequencing procedures. DNA isolation and PCR development of libraries for sequencing will be carried out using microbiome optimized, clean technique and microbial free reagents.

**16S rRNA Sequence Analysis:** Methods for microbial composition analysis will follow the general approaches described by Caporaso and Sun relying on two separate strategies, taxonomy-independent and -dependent analyses. Taxonomy-independent analysis provides a basic description of the bacterial composition defined in operational taxonomic units (OTU), while taxonomy-dependent analysis relates the bacterial composition (OTU data) to known bacterial classifications defined by shared characteristics of bacterial groups (taxonomy). This two-pronged approach allows analysis of known bacteria using reference databases and discovery of unknown bacteria in the sample. This aspect of the MiSeq sequence analysis allows for more complete characterization of bacterial composition than older available technology used in previous studies.

Prior to either analysis, the data will be pre-processed for error-correction to remove low quality reads. A BLAST search will assign sequences to known reference sequences using regularly updated databases. Analyses will be performed to group sequences into an OTU table using computational methods developed by members of our group. The OTU table provides a global view of the bacterial composition comprising the microbiome. The 2000-processor Dell P4 (64-bit) Linux cluster at UB's Center for Computational Research (CCR) can process the large quantity of data generated in this pilot project.

**Data Analysis:** Statistical procedures will be limited to descriptive analyses in this pilot study. Following the 16S rRNA sequencing and data reduction steps, we will describe the subgingival microbiome composition and relative abundance (OTU table). To begin to understand potential differences in the groups, univariate statistical analysis and descriptive statistics will be performed to identify oral bacteria associated with diabetes status and treatment group. Numerical, graphical (boxplots, scatterplots), and formal

**comparisons (Student's t-test, ANOVA, regression, or non-parametric equivalents for sparse bacteria) will be produced for visualization of results. Other analytic techniques will be utilized as well.**

**Descriptive statistics as well as univariate statistical analysis will be performed to identify oral bacteria associated with diabetes status and treatment group. Multivariable logistic regression will be conducted to control for other risk factors. Principal Component Analysis (PCA) or Hierarchical Cluster Analysis (HCA) also will be used to further understand potential associations with diabetes status and treatment group.**

**The analyses planned for this pilot study will provide preliminary data for preparation of a larger more definitive study.**

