**Primary Endpoints:**

1. **Change in Probing pocket depth (PPD) at the 6-month post-SRP completed at Baseline.**

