**Secondary Endpoints:**

1. **Oral clinical variables:** Changes in Bleeding on Probing (BOP), Clinical attachment level (CAL), and Gingival Index and Plaque Index (PI) at 3, 6, 9, and 12 months after treatment (Baseline); Change in PPD at 3, 9, and 12 months after treatment.
2. **Systemic variables:** Changes in Hemoglobin A1c (HbA1c); Fasting blood glucose (FBG); Immunoreactive insulin (IRI); High sensitivity C-reactive protein (hs-CRP); at 3, 6, and 12 months after treatment. Blood for C-peptide; proinsulin; total GLP-1, PYY, dipeptidyl peptidase-IV (DPP-IV); glucagon; plasma endotoxin (LPS); soluble TNF- $\alpha$  RI and RII; the dicarbonyl methylglyoxal (MGO), and Trimethylamine-N-Oxide (TMAO) will be collected at 3, 6, and 12 months study visits, but tested later.
3. **Microbiology endpoints:** Changes in Subgingival salivary and gut microbiome after periodontal treatment (SRP or SRP + SPT). Changes in the skin and vaginal microbiome after treatment will be assessed as resources permit.

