**Response:**

**A minimum of 104 subjects will be enrolled in the study, with at least 26 participants per group. The study was powered to detect a difference in probing pocket depth (PPD) of 35% between groups, and a standard deviation (SD) of 0.5 for the distribution of 6 month changes. A sample size of 24 per group was estimated assuming approximately 80% power (alpha = 0.05). A minimum 26 subjects per group with an attrition rate of 10% will be enrolled in this study.**

**10-14-2021: We are continuing recruitment to greater than 100 participants in order to balance the numbers of participants per cell, to increase the size of the control group (no perio disease and no diabetes), and to increase the numbers with diabetes but no perio disease so that we have a more solid base on which to complete vigorous data analyses.**

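### Section 17.1 gives no analysis of 6-month PPD change, the sole primary endpoint for which Section 17.2 claims power, and the powered contrast is not named

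*Combined protocol and SAP*

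**What the plan says.** Section 2.1 lists one primary endpoint: "Change in Probing pocket depth (PPD) at the 6-month post-SRP completed at Baseline". The clinical part of Hypothesis 1 (Section 1.2) predicts a better clinical result with SPT added to scaling and root planing (SRP) than with SRP alone. The main goal in Section 1.1 concerns people with type 2 diabetes; the second goal compares the response to therapy with and without diabetes.

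Section 17.2 states: "The study was powered to detect a difference in probing pocket depth (PPD) of 35% between groups". It gives an SD of 0.5 for 6-month changes and adds: "A sample size of 24 per group was estimated assuming approximately 80% power (alpha = 0.05". It names no pair of groups, no base for the 35%, no unit for the SD and no sidedness.

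Section 17.1 opens with 16S sequencing. Its data analysis paragraph begins "Statistical procedures will be limited to descriptive analyses in this pilot study" and continues with the sequencing output. It then lists t-tests, ANOVA and regression, or non-parametric equivalents for sparse bacteria. The stated target is that these analyses "will be performed to identify oral bacteria associated with diabetes status and treatment group". It adds "Multivariable logistic regression will be conducted to control for other risk factors" without naming the outcome. PPD and the other clinical endpoints do not appear.

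In Section 10.1, the 3-month visit (item 9) provides for repeat treatment of sites that have not improved. The 6-month visit (item 7) says rescue therapy will be taken into account in the analysis. Section 17.1 does not say how.

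**The concern.** A primary endpoint and a power claim imply a planned comparison of PPD between named groups, and the analysis section contains none. If a PPD test is added later, the contrast, the covariates, and the handling of retreated and missing participants can all be chosen after the data are seen. A reader of the report could not tell whether a PPD result is the one the trial was sized for or part of a pilot description.

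**Working it through.** **1. The passages side by side.** Sections 2.1, 1.2 and 17.2 require a between-group comparison of PPD change. Section 17.1 has two possible readings:

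- The descriptive sentence covers only the microbiome work. Then no primary analysis is stated.
- It covers all statistics. Then the test powered in Section 17.2 is excluded.

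Neither reading contains the powered comparison.

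**2. The plan's own figure.** Inputs from Section 17.2: SD 0.5 (mm assumed), alpha 0.05, about 80% power, 24 per group. By the normal approximation, n per group = 2 × (z_alpha + z_power)² × 0.5² / d².

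- If 35% is read as d = 0.35 mm, two-sided: 2 × (1.960 + 0.842)² × 0.25 / 0.1225 = 32.0, reported as 33 after rounding up on unrounded z-values and confirmed by the t-test (33.02). This does not give 24.
- The same d, one-sided: 2 × (1.645 + 0.842)² × 0.25 / 0.1225 = 25.2, so 26. This is close to 24.
- If 35% is relative, two-sided: 24 per group corresponds to d = 0.404 (normal) or 0.413 (noncentral t). The reference change is then 0.404/0.35 = 1.16 mm or 0.413/0.35 = 1.18 mm.

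The 24 therefore cannot be reproduced uniquely from what the documents state.

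**3. What each contrast could detect.** Noncentral t, two-sided 0.05, 80% power, no baseline adjustment, n per group:

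| Contrast | SE | SE at n = 24 | df | Detectable at 24 | 95% CI half-width at 24 | Detectable at 26 |
|---|---|---|---|---|---|---|
| A vs C | 0.5√(2/n) | 0.144 | 46 | 0.413 | 0.291 | 0.396 |
| SPT pooled over diabetes status | 0.5√(2/(2n)) | 0.102 | 93 | 0.289 | 0.203 | 0.277 |
| SPT × diabetes | 0.5√(4/n) | 0.204 | 92 | 0.578 | 0.405 | 0.555 |

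The n = 26 column is shown because Section 5.1 counts 26 per group with complete data, whereas Section 17.2 counts 26 enrolled with 10% attrition (26 × 0.9 = 23.4). Reading A vs C from a four-cell model raises the degrees of freedom and changes 0.413 only to 0.409.

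**4. Illustrative power.** Assuming SRP-only changes of 0.75, 1.0 and 1.5 mm, 35% is 0.26, 0.35 and 0.53 mm. At 24 per group, power is 43%, 66% and 95% for A vs C, and 72%, 92% and over 99% pooled.

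**5. Baseline adjustment.** Relative to the change score, the variance ratio is (1 − r²)/(1 + k² − 2rk), where r is the baseline to 6-month correlation and k the baseline SD divided by the 6-month SD. Both are assumed. At r = 0.5, k = 0.5 the ratio is 0.75/0.75 = 1, so A vs C stays at 0.413. At r = 0.3, k = 1.25 it is 0.91/1.8125 = 0.502, giving 0.413 × √0.502 = 0.293.

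**The case against.** **Scope of the descriptive sentence.** It introduces the microbiome paragraph and can fairly be read as covering that work alone. A reader might infer that the plan forbids a PPD test. The text does not establish that, but on the narrow reading the primary analysis is still missing.

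**The listed tests.** It could be said that ANOVA and regression already cover PPD. They stand in the microbiome paragraph and are never tied to PPD.

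**The contrast.** Sizing per group for a difference between groups most naturally describes two single groups. With the main goal in diabetics, that points to A vs C. This stands. The spread from 0.289 to 0.578 should not be read as uncertainty about what Section 17.2 meant, since nothing there describes a pooled or interaction test. It shows what is at stake if the contrast is chosen later. The two-to-one ratio is itself a property of any balanced 2 × 2 design.

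**The 2021 note.** A reader might take "so that we have a more solid base on which to complete vigorous data analyses" as a further conflict with descriptive analysis. It is not. The note extends recruitment partly to people without periodontal disease, who fall outside inclusion criterion 5 and are not assigned there to Groups A to D. It mentions neither PPD nor hypothesis testing.

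**The base of the 35%.** Section 17.2 cites a published trial, and the base may be given there. The power figures therefore do not show that the trial is underpowered.

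**Pilot status.** Sections 6.4 and 17.1 call the study a pilot. A descriptive pilot is legitimate, but the power claim must then be reworded.

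**Conclusion.** The point holds as an omission and an internal inconsistency: the sole primary endpoint has no stated analysis, and the powered contrast is unnamed. This rests on the wording of Sections 1.2, 2.1, 17.1 and 17.2 and needs no numerical assumption.

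Its size does need assumptions: SD 0.5 in mm, two-sided 0.05, equal groups and no baseline adjustment. Across the three contrasts that the goals and hypothesis suggest, the detectable difference runs from 0.289 to 0.578 at 24 per group, and from about 0.28 to 0.56 at 26. Power for the 35% is illustrative only.

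Retreatment is a related gap. It can begin at 3 months, before the primary measurement, and its promised place in the analysis is not specified. The documents do not show in which direction, or by how much, it would move the PPD comparison. This should be settled before PPD is compared by group.

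**What to change.** 1. In Section 17.1, restrict the descriptive sentence to the microbiome analyses and call those exploratory, including their formal tests.
2. Add one primary analysis: a linear model of participant-level 6-month PPD in participants randomised to Groups A to D, as allocated, with terms for SPT, diabetes status, SPT × diabetes and baseline PPD. Use the PPD summary to which the SD of 0.5 refers. With baseline in the model, the group contrast is the same as for change in PPD, so the endpoint is unchanged.
3. Name A vs C, two-sided, as the primary contrast. It matches the main goal and the per-group sizing. Make Section 17.2 refer to it. Report the SPT effect averaged over diabetes status and the SPT × diabetes interaction as secondary estimates with 95% CI.
4. Label A vs B and C vs D as non-randomised comparisons, since diabetes status cannot be assigned.
5. Report retreatment from the 3-month visit by arm, and state in Section 17.1 how it and missing 6-month PPD enter the analysis.

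If pilot status is preferred, use the same model for estimation only, with an expected unadjusted 95% CI half-width of about 0.29 for A vs C at 24 per group, and reword the power statement to match.

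The cost is wording and one regression; baseline and 6-month PPD are already collected. The downside is commitment to one contrast, and A vs C is less precise than the pooled SPT effect (0.413 against 0.289). Baseline adjustment may recover some of that loss or none, depending on a correlation and SD ratio that the documents do not give.
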